**Investigators:**

1. [name]
2. [name]
3. [name]

**Describe the background and rationale for this project. Reference to peer reviewed literature is desirable:** With the evolution of technology, many types of intra-abdominal surgery in infants and children are performed using laparoscopy. Despite the benefits of such techniques in regards to postoperative recovery and pain when compared to open laparotomy, the insufflation of the peritoneum with CO2 increases in intra-abdominal pressure (IAP) which may impact cardiac output, organ perfusion, and tissue oxygenation.

**How will your study be funded:** No funding is required for this study.

**Provide a potential start date for your study to be included in the IRB application:** Start date: April 1, 2016 – End date: April 1, 2018

**Describe the significance of the proposed research:** Although generally safe and effective, the increase in IAP during laparoscopy may increase systemic and pulmonary vascular resistance and decrease cardiac output. In addition to that, there are other factors which can effect on the organ oxygenation during pneumoperitoneum (e.g. hypercarbia, Trendelenburg position). Although blood pressure is maintained, there may be decreases in cardiac output and hence organ oxygen delivery. The current study will assess the effect of laparoscopy on tissue oxygenation in the patient population. Tissue oxygenation will be assessed non-invasively using near infrared spectroscopy (NIRS device: INVOS 5100B; Somanetics, Troy, MI, USA), a device that is commonly used in our operating rooms to assess cerebral and tissue oxygenation.

**State the primary and secondary objectives of the study:**

1. To evaluate changes in tissue and cerebral oxygenation during laparoscopic pyloromyotomy.

**If this research is hypothesis driven, succinctly state the hypothesis:**

Laparoscopy will decrease tissue and cerebral oxygenation.

**Outline the major steps and methodologies in the clinical protocol.**

This prospective study will include 50 patients under the age of 18 years who are having laparoscopic pyloromyotomy. There will be no change in the anesthetic or perioperative care of these patients. Tissue and cerebral oxygenation will be monitored using near infrared spectroscopy (NIRS). Prior to anesthetic induction, the NIRS monitor will be placed on the forehead. The device is non-invasive like pulse oximetry

using a non-painful adhesive sticker. The device can be applied to different sites on the body to measure cerebral, tissue or even organ oxygenation. For the purpose of the study, we will place one monitor on the forehead to measure tissue oxygenation and a second over the lower back to measure tissue (muscle or renal) oxygenation. These devices are used routinely in the operating room and the cardiothoracic intensive care unit for cardiac patients. Although not used on every surgical procedure, NIRS monitoring can be used on all patients who are undergoing major surgical procedures. Tissue and cerebral oxygenation will be recorded continuously starting just prior to anesthetic induction until the completion of the procedure.

**Identify the variables to be measured and how they will be statistically evaluated:** Changes in tissue/renal and cerebral oxygenation will be compared at various times throughout the procedure using analysis of variance. The specific times will be baseline (prior to induction), after anesthetic induction and prior to insufflation, during insufflation, and after insufflation is completed. The data will be also downloaded from the device and analyzed using analytical tool provided by the company. Demographic information such as medical record number, date of service, date of birth, gender, birth weight and week, ASA, height, weight, BMI, and diagnosis will be recorded. We will also record preoperative lab values, anesthesia time, procedure time, pneumoperitoneum time, vital signs and ventilator settings during the surgery.

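### Does leaving the lower-back sensor's target as muscle or kidney, with no landmark and no record of position, undermine the tissue outcome?

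*Combined protocol and SAP*

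**What the plan says.** The objectives section gives one aim: "To evaluate changes in tissue and cerebral oxygenation during laparoscopic pyloromyotomy". The hypothesis section gives one hypothesis: "Laparoscopy will decrease tissue and cerebral oxygenation". Neither names the kidney.

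The outline of steps and methods puts the second sensor as "a second over the lower back to measure tissue (muscle or renal) oxygenation". It also says of the monitor: "The device can be applied to different sites on the body to measure cerebral, tissue or even organ oxygenation". Recording is continuous from just before induction to the end of the procedure, in 50 patients.

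The paragraph on variables and their evaluation says that "Changes in tissue/renal and cerebral oxygenation" are compared by analysis of variance at four times: baseline, after induction but before insufflation, during insufflation, and after it. The data to be collected are demographics and then: "We will also record preoperative lab values, anesthesia time, procedure time, pneumoperitoneum time, vital signs and ventilator settings during the surgery". Sensor position is in neither list.

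The significance paragraph raises the worry that "there may be decreases in cardiac output and hence organ oxygen delivery", and then says that the study will assess tissue oxygenation. Once, in the methods, the forehead sensor is described as "one monitor on the forehead to measure tissue oxygenation".

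**The concern.** By its own account the plan treats site as deciding what is measured, and it separates tissue from organ. Yet it leaves the lower-back target as either of two tissues, fixes no level or side, and keeps no record of where the sensor went. The label also shifts: tissue in the objective and hypothesis, muscle or renal in the methods, tissue/renal in the analysis.

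The stake is attribution. If some sensors sample mainly muscle and others mainly kidney, or if each reading blends the two, a fall might come from muscle alone, and a null might hide a kidney effect. The significance paragraph and the word renal in the analysis both invite an organ-level reading. Position that is not written down at the time cannot be recovered afterwards, so no later analysis by position would be possible.

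**Working it through.** **1. What the plan sets out to claim.** Set side by side, the objective and hypothesis speak of tissue and cerebral oxygenation. Renal appears only in the methods parenthesis, as one of two possibilities, and in the analysis label. The organ-delivery remark is background, and the sentence after it names tissue oxygenation as what is assessed. The plan announces no kidney-specific conclusion.

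**2. What unrecorded position does to the comparison.** Write the reading of patient *i* at time *t* as Y(i,t) = a(i) + c(i,t), where a(i) is the level set by that patient's sensor position and c(i,t) is the change since baseline, with c(i,0) = 0. Then Y(i,t) − Y(i,0) = c(i,t), and a(i) drops out. This takes the sensor as staying in place, which continuous recording suggests and nothing contradicts, and takes the analysis of variance as respecting the repeated measurements. Position then matters only if muscle and kidney respond differently. The documents do not say whether they do.

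**3. Size, on assumed inputs.** The plan gives no alpha, power, effect size or SD with its 50 patients, so there is no figure to reproduce. For illustration:

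- Two-sided 5% paired *t* test between two times, n = 50, SD of change 1. The four-time analysis of variance is not modelled.
- Kidney change d = 0.404 SD, chosen because it gives 80% power at n = 50.
- Share p of sensors over muscle; muscle change r × d.
- Mean change = d(1 − p + pr). Variance = 1 + p(1 − p)d²(1 − r)².

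With p = 0.5 and r = 0, the mean is 0.404 × 0.5 = 0.202 and the variance is 1 + 0.25 × 0.404² = 1.041. The standardised effect is 0.202/√1.041 = 0.198, and power is 28%.

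| Share over muscle | r = 0 | r = 0.5 | r = 1 | r = 1.5 |
|---|---|---|---|---|
| 0.25 | 54% | 69% | 80% | 88% |
| 0.50 | 28% | 55% | 80% | 94% |
| 0.75 | 11% | 41% | 80% | 97% |

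If every reading is instead a half-and-half blend (variance 1), the figures are 29%, 56%, 80% and 94%, so the pattern does not depend on tissue differing between patients.

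The result also depends on the effect chosen. With p = 0.5 and r = 0.5, power is 55% at d = 0.404, 73% at 0.5 and 98% at 0.8.

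In the reverse case the kidney does not change and muscle changes by 0.404 SD in half the patients. The formula is symmetric at p = 0.5, so the test is significant about 28% of the time. That would be a false statement about the kidney but a true one about lower-back tissue.

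**4. What a landmark would add.** It would make position uniform. It would not show whether the signal comes from muscle or kidney, so neither a landmark nor an analysis limited to patients at the landmark would support a renal conclusion. The limited analysis would also have less power: at d = 0.404, about 76% with 45 patients, 70% with 40 and 64% with 35.

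**The case for a change.** The strongest case for a change is that the lower back is one of only two measured sites, the analysis sentence uses the word renal, and the rationale is about organ delivery, so readers will draw an organ-level conclusion that the methods cannot support. A placement sentence, a data field and one consistent label would cost almost nothing, and lost position data stay lost.

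The textual part of this stands. The label is inconsistent, position is not listed, and the plan does not say that staff would place the sensor uniformly. A kidney-specific reading is unsupported.

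What does not stand is the step from there to a fault in the planned analysis. The argument shows that one possible interpretation should be avoided; the stated hypothesis can still be answered. The wording muscle or renal can fairly be read as an open admission that the sensor may sample either. Recording position would allow a description of placement, but it would not supply the missing attribution. Calling the forehead reading tissue is a clerical slip, because the same section separately names cerebral oxygenation as monitored, recorded and analysed.

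**Conclusion.** No change to the plan is needed. This is a gap in detail and labelling that an analyst fills sensibly by reporting the second outcome as within-patient change in regional lower-back saturation, with no claim about the kidney. The objective and hypothesis can be answered on that footing, and the cerebral outcome is not affected.

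One limit remains for interpretation: neither a change nor a null at this site can be assigned to the kidney. The documents fix neither the direction nor the size of any distortion. The span of 11% to 97% rests wholly on assumed values for the kidney effect, the share of sensors over muscle and the muscle response, and it describes power for a renal effect that the plan does not set as its target. The conclusion assumes that each sensor stays in place through the procedure, that the analysis respects the repeated measurements, and that no renal claim is made. If a kidney-specific conclusion became an aim, the point would carry real weight.

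### No key contrast and no one-site-or-both rule: the chance of a false oxygenation decrease runs from under 1% to about 22%, depending on choices left open

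*Combined protocol and SAP*

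**What the plan says.** The objectives section lists a single aim, not labelled primary or secondary: "To evaluate changes in tissue and cerebral oxygenation during laparoscopic pyloromyotomy". The hypothesis section gives a direction and joins the two sites: "Laparoscopy will decrease tissue and cerebral oxygenation".

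The methods section sets the size and the measurements: "This prospective study will include 50 patients under the age of 18 years who are having laparoscopic pyloromyotomy", and "we will place one monitor on the forehead to measure tissue oxygenation and a second over the lower back to measure tissue (muscle or renal)". The paragraph on variables and their statistical evaluation gives the test, "Changes in tissue/renal and cerebral oxygenation will be compared at various times throughout the procedure using analysis of variance", and the times: "The specific times will be baseline (prior to induction), after anesthetic induction and prior to insufflation, during insufflation, and after insufflation is completed". It then adds: "The data will be also downloaded from the device and analyzed using analytical tool provided by the company".

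The document states no significance level, sidedness, repeated-measures form, follow-up test, multiplicity adjustment or key contrast. It does not say how a result that differs between the two sites would be read, or how the vendor-tool analysis ranks against the ANOVA.

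**The concern.** The test named does not answer the hypothesis. A four-time ANOVA asks whether the means differ anywhere, in any direction. To conclude that laparoscopy lowered oxygenation, someone must choose a pair of times, look at the sign, and decide whether one site is enough. The plan leaves all three steps open.

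The pre-induction time makes this worse. If induction itself moves the readings, the ANOVA can be significant when insufflation does nothing, so a significant result is not evidence about laparoscopy.

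Two things are at stake. The false-positive rate of the study's only hypothesis is undefined until these choices are made, and they could be made after the data are seen. A split result, with one site falling and the other not, could be reported as confirming or as refuting the same sentence.

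**Working it through.** The plan gives no error rate or power to reproduce, so the check is how far the false-decrease rate moves across the readings the text leaves open.

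**Inputs from the protocol.** 50 patients in one group, 2 sites, 4 times. Pairs of times per site: 4 × 3 / 2 = 6, so 12 over both sites.

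**Assumptions (not in the protocol).** Two-sided 5% per test; correlation 0.5 between times within a site; correlation 0 to 0.6 between sites, with 0.9 as an extreme; normal data; none missing. Each setting was simulated with 20,000 or more trials, using paired t-tests and a repeated-measures F test per site.

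**Closed-form checks.**
- Either of two independent ANOVAs significant: 1 − 0.95² = 9.75%.
- A false fall at either of two independent sites for one contrast, with 2.5% in the falling direction: 1 − 0.975² = 4.9%.
- Any of 12 independent tests significant: 1 − 0.95¹² = 46.0%. This is an upper bound, because the pairs share data.

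**Simulated rates, no true effect at any time.**

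| Reading of the plan | Between-site correlation 0–0.6 | Correlation 0.9 |
|---|---|---|
| Fall at both sites, during versus just before insufflation | under 1% | 1.6% |
| Fall at either site, same contrast, unadjusted | about 4–5% | – |
| Any falling pair at a site whose ANOVA is significant | about 6–7% | 4.8% |
| Either ANOVA significant, any direction | 9–10% | 7.0% |
| Any of 12 unadjusted pairs a significant fall | about 20–22% | 15.8% |
| Any of 12 unadjusted pairs significant, any direction | 33–37% | 27% |

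Sidedness is also unstated. With one-sided 5% tests, the chance of any false fall among the 12 pairs is 33–38% (28% at correlation 0.9).

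**Induction alone shifts values.** All three later times were moved together relative to baseline, by an assumed 0.3 to 1 SD, with no insufflation effect. The ANOVA is then usually significant. A false fall among the three later times, counted only at a site with a significant ANOVA, occurs in about 10–13% (9% at correlation 0.9 with a 1 SD shift).

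**A true effect at both sites.** Take a fall of 0.404 SD of the paired difference, chosen because it gives 80% power per site with 50 patients. With independent sites:
- either site significant: 1 − 0.20² = 96%
- both sites significant: 0.80² = 64%
- exactly one significant: 96 − 64 = 32%

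At between-site correlation 0.6 these are about 90%, 70% and 20%. A split is therefore common at this effect even when the hypothesis is true. The gap depends heavily on the effect: for independent sites it is 2 × power × (1 − power), or about 41 points at 0.2 SD, 12 at 0.5 SD and 3 at 0.6 SD. If only one site truly falls by 0.404 SD, the either-site rule succeeds in about 80% of trials and the both-sites rule in about 2%.

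**The case against.** A reader might infer that the plan, carried out as written, makes a chance decrease far likelier than 5%. The document does not support that. It names ANOVA and nowhere plans 12 unadjusted pairwise tests. With ANOVA as a gate and no effect at any time, the rate is about 6–7%; at the insufflation contrast alone it is 5% or less.

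The hypothesis wording also restrains interpretation. A fall between baseline and the post-induction time comes before insufflation, so it cannot be evidence about laparoscopy. The conjunction in "Laparoscopy will decrease tissue and cerebral oxygenation" can fairly be read as requiring both sites. These points stand, and they are why the result is a range. They do not close the gap: the both-sites reading is permitted but never made a rule, the follow-up to the ANOVA is unstated, and the gate gives limited protection once induction moves the readings.

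A reader might also count the vendor tool as a second set of hypothesis tests. Nothing says that it produces p-values; it may only summarise. It is an unranked second route of unknown size.

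Finally, this is a small, unfunded, single-group study that does not alter care, and its objective is only to evaluate changes. That argues for a light remedy. It does not remove the need for one, because the study states a directional hypothesis and labels no comparison descriptive.

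**Conclusion.** The concern holds in a conditional form. The plan ties a directional two-site hypothesis to a non-directional four-time test, with no key contrast and no rule for one site versus both. With no true effect, the false-decrease rate runs from under 1% (both sites, insufflation contrast), through about 5% (either site, same contrast) and 6–7% (any pair after a significant ANOVA), to about 20–22% (any of 12 unadjusted pairs). It is about 10–13% among the three later times if induction alone shifts values, even with the ANOVA as a gate.

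These figures rest on an assumed two-sided 5% level, between-site correlation of 0 to 0.6, complete data and, for the last, a shift of 0.3 to 1 SD. The defect is that an unstated choice sets the rate; no single inflated rate is established. This should be settled before analysis.

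**What to change.** Add a short analysis statement before any data are analysed:

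1. **Key contrast.** At each site, compare the reading during insufflation with the one after induction but before insufflation, within patient. Naming the reference time matters, because using the pre-induction baseline would mix the effect of induction with that of insufflation.
2. **Decision rule.** Use Hochberg's procedure over the two sites. If both show a fall with two-sided p ≤ 0.05, the joint hypothesis is supported. Otherwise a fall at one site needs p ≤ 0.025 and is reported as a finding for that site only. Two falls at p = 0.04 support the joint hypothesis; one fall at p = 0.04 with no significant fall at the other site supports no claim.
3. **Other time pairs.** Report them descriptively with confidence intervals.
4. **Vendor tool.** Use it for export and descriptive summaries; base inference on the exported readings.

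The cost is a few sentences, with no added data and no change to care. The downside is power. At an assumed 0.40 SD fall, if only one site truly falls, power for that site drops from 80% to about 71%; if both fall, the joint claim has about 64–70%. These figures change with the assumed effect, for which the protocol gives no value.

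### The hypothesis is that laparoscopy lowers oxygenation, but the only named test is an analysis of variance over four times, one of them before induction, with no insufflation contrast and no repeated-measures form stated

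*Combined protocol and SAP*

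**What the plan says.** The hypothesis section is directional: "Laparoscopy will decrease tissue and cerebral oxygenation". The objectives section is broader: "To evaluate changes in tissue and cerebral oxygenation during laparoscopic pyloromyotomy".

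The paragraph on variables and statistical evaluation says that changes at the two sites "will be compared at various times throughout the procedure using analysis of variance", and then: "The specific times will be baseline (prior to induction), after anesthetic induction and prior to insufflation, during insufflation, and after insufflation is completed". It names no pair of these times as the test of the hypothesis and does not say whether the analysis of variance is repeated-measures. It adds that downloaded data will go through the device company's analytical tool, but gives no method, model or contrast for that tool.

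The data are paired by design. The methods section states: "Tissue and cerebral oxygenation will be recorded continuously starting just prior to anesthetic induction until the completion of the procedure". The sample is a single group: "This prospective study will include 50 patients under the age of 18 years who are having laparoscopic pyloromyotomy". No alpha, power, effect size, SD or correlation is given.

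**The concern.** Two events lie between the first and third readings: induction of anesthesia and insufflation. An overall test over all four times asks whether any mean differs from any other. That suits the objective of evaluating changes. It does not by itself answer the hypothesis, because a shift at induction is enough to make it significant. The reading that separates the two events, after induction and before insufflation, is collected but given no role in the analysis.

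The unstated form of the ANOVA matters as well. Every patient contributes to all four times, so an ordinary one-way ANOVA leaves between-patient variation in the error term. With positively correlated readings that makes the test conservative and costs power.

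The two risks belong to different readings of the same sentence. Under the repeated-measures form, a positive result may be credited to laparoscopy when induction produced it. Under the one-way form, a real fall may be missed. With four times and two sites, leaving the deciding comparison unnamed also allows it to be chosen after the data are seen.

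**Working it through.** **Inputs.** From the document: n = 50, four times, one group. Assumed, because the document gives none of them: two-sided alpha 0.05, equal correlation ρ between times, SD of within-patient change 8, 10 or 15 points, and shifts of 2, 3 or 5 points. The plan has no power figure to reproduce.

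**1. Overall repeated-measures F when only induction acts.** The means are (0, d, d, d). The squared deviations from their average sum to 0.75d². The error variance is (SD of change)²/2. The noncentrality is therefore λ = 50 × 0.75d² / [(SD of change)²/2], on 3 and 147 degrees of freedom. At SD of change 10, λ = 0.75d², that is 3.0, 6.75 and 18.75 for d = 2, 3 and 5.

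| SD of change | d = 2 | d = 3 | d = 5 |
|---|---|---|---|
| 8 | 41% | 77% | >99% |
| 10 | 27% | 56% | 96% |
| 15 | 14% | 27% | 66% |

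Entries are rejection rates with no insufflation effect. The paired contrast (during insufflation minus after induction and before insufflation) has true mean zero here and rejects in about 5% (4.7% to 5.5% in simulation).

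**2. Ordinary one-way ANOVA on the same paired readings.** The test is F on 3 and 196 degrees of freedom, with 20,000 simulated trials per cell.

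- No change at any time, ρ = 0.5: it rejects in about 0.2%, not 5%.
- A 5-point fall during insufflation with recovery, means (0, 0, −5, 0), total SD held at 10. The SD of change is 10√[2(1−ρ)], which gives 10.0, 7.7 and 6.3 at ρ = 0.5, 0.7 and 0.8:

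| ρ | One-way ANOVA | Repeated-measures F |
|---|---|---|
| 0.5 | 72% | 96% |
| 0.7 | 72% | >99% |
| 0.8 | 74% | >99% |

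- The same fall with the SD of change held at 10 instead. The total SD is then 10/√[2(1−ρ)], which gives 10.0, 12.9 and 15.8. One-way power is about 72%, 29% and 6%.

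The one-way form loses power under either convention. How much it loses depends on which SD is held fixed.

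**3. What the direct contrast costs.** For a 5-point fall its noncentrality is 5√50 / SD of change: 3.54 at SD 10 and 2.36 at SD 15, on 49 degrees of freedom. Power is 93% and 64%. The repeated-measures F gives 94–99% and 61–80% for the same fall, taken over an induction rise of 0, 3 or 5 points, with or without recovery afterwards.

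**The case against.** The strongest reply is that the plan is brief, not wrong. Speaking of changes, in patients who are recorded continuously, suggests within-patient comparison. Comparing the times suggests more than stopping at an overall F. Nothing excludes follow-up comparisons, and the time-point means would show direction. The four-time comparison also fits the stated objective. All of this stands, and it limits the point to a gap in specification. It does not close the gap: no comparison is named as decisive, and the repeated-measures form, if intended, is the one more likely to reject because of induction alone.

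A second reply concerns the one-way figures. A reader might infer that such an analysis would almost always miss a real fall, citing 29% or 6%. The document does not support that. Those values require total SDs of 12.9 and 15.8 points, for which it offers no evidence; with a total SD of 10, power is about 72–74%. The loss is real, but a near-total collapse is not a general result.

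A third temptation is to say that even the direct contrast fails, because the significance section notes that "there are other factors which can effect on the organ oxygenation during pneumoperitoneum (e.g. hypercarbia, Trendelenburg position"). But the hypothesis concerns laparoscopy, not intra-abdominal pressure alone, and changes that accompany pneumoperitoneum can fairly be counted as part of the technique. This is a caveat on interpretation, not a flaw in the contrast.

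**Conclusion.** The point holds as a gap between the hypothesis and the named test, and it should be fixed. The analysis of variance as written answers whether anything changed across the procedure; the hypothesis asks whether laparoscopy lowered oxygenation. At an assumed SD of change of 10, an induction-only shift of 2 to 5 points makes a repeated-measures F significant in 27% to 96% of trials, against 5% for the insufflation contrast. If the ANOVA were run as ordinary one-way, it would be conservative and would give up roughly a quarter of its power for a 5-point fall at total SD 10, and more if the SD of change stays at 10 as correlation rises.

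Every SD, correlation, effect size and alpha here is an assumption; only the 50 patients come from the document. A reader might conclude that the study cannot test its hypothesis. That would go too far: the readings it needs are already planned, and the wording leaves room for the right comparison.

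**What to change.** In the paragraph on variables and statistical evaluation:

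- Name as the primary analysis, at each site, the within-patient difference between the reading during insufflation and the reading after induction but before insufflation. Take it from a paired analysis or a repeated-measures model and report it with a 95% confidence interval.
- Because recording is continuous, fix one summary per period in advance, for example the period mean.
- Make the comparisons with the pre-induction and post-insufflation readings secondary.
- Say that neither the overall F nor an ordinary one-way ANOVA is the test of the hypothesis.

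Three additions are optional: whether a fall is required at both sites or at either; a sentence that, without a control group, the contrast removes the induction step but not changes concurrent with insufflation; and a table, at the same times, of the vital signs and ventilator settings the plan already records.

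The cost is a few sentences, with no new patients or oxygenation readings. The contrast has slightly less power than a repeated-measures F in most scenarios: for a 5-point fall, 93% against 94–99% at SD of change 10, and 64% against 61–80% at SD 15.

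### Must the vital signs and ventilator settings be tied to the four analysis times before a fall in oxygenation can be read as an effect of laparoscopy?

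*Combined protocol and SAP*

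**What the plan says.** The section *Identify the variables to be measured and how they will be statistically evaluated* gives the main analysis: "Changes in tissue/renal and cerebral oxygenation will be compared at various times throughout the procedure using analysis of variance". It then fixes four times for that comparison: "The specific times will be baseline (prior to induction), after anesthetic induction and prior to insufflation, during insufflation, and after insufflation is completed". A second analysis uses the manufacturer's software: "The data will be also downloaded from the device and analyzed using analytical tool provided by the company".

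Vital signs and ventilator settings appear once, in a list of items to be collected: "We will also record preoperative lab values, anesthesia time, procedure time, pneumoperitoneum time, vital signs and ventilator settings during the surgery". The list gives no time, frequency or named settings. Neither described analysis uses them.

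Four other places bear on the point:

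- The outline of the clinical protocol leaves ventilation to usual care: "There will be no change in the anesthetic or perioperative care of these patients".
- The objective is descriptive: "To evaluate changes in tissue and cerebral oxygenation during laparoscopic pyloromyotomy".
- The hypothesis is causal and directional: "Laparoscopy will decrease tissue and cerebral oxygenation".
- The significance section accepts that pressure is not the only influence: "there are other factors which can effect on the organ oxygenation during pneumoperitoneum (e.g. hypercarbia, Trendelenburg position".

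**The concern.** There is one group and no control, so anything attributed to laparoscopy rests on comparing phases within each infant. Whatever else differs between phases enters that comparison. Hypercarbia and position can be regarded as part of laparoscopy. Inspired oxygen cannot, and the study does not hold it constant.

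If inspired oxygen were lower during insufflation than just before it, saturation would fall in the hypothesised direction with no effect of laparoscopy. If it were higher, a real fall would be partly hidden. At stake is whether a reader could tell these cases apart. Oxygenation is recorded continuously, but nothing expressly secures a ventilator reading after induction and before insufflation, and a reading missed there might not be recoverable.

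**Working it through.** **What the text settles.** The plan has no figure to reproduce. It gives 50 patients, without alpha, power, effect size or SD. Set side by side, the passages show:

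1. The four times are attached to oxygenation only. Ventilator settings and vital signs are attached to the surgery as a whole.
2. The settings are nevertheless to be recorded. If entries carry a clock time, they can be aligned with the four times afterwards. What is missing is pre-specification; the documents do not show that data will be missing.
3. Inspired oxygen is not named anywhere. Counting it among the ventilator settings is an assumption, though a reasonable one.
4. The plan does not single out a pair of times. Before versus during insufflation is inferred from the hypothesis.
5. The objective asks for changes during the procedure, and the unadjusted change answers it. Only the causal sentence in the hypothesis is exposed.

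**How large could the bias be?** Only n = 50 comes from the protocol. The other inputs are assumed: 50 complete pairs, a two-sided 5% paired t-test (49 degrees of freedom, critical value 2.01), no true laparoscopy effect, a share p of infants whose inspired oxygen changes in one direction, an effect of d points in each of them, and a residual SD s of the within-infant change.

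- Mean shift = p × d
- Total SD = √(s² + p(1 − p)d²)
- Noncentrality = √50 × shift / total SD

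Worked case, p = 0.5, d = 5, s = 10: shift 2.5; total SD = √(100 + 0.25 × 25) = 10.31; noncentrality = 7.071 × 2.5 / 10.31 = 1.71; rejection probability 0.390.

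| Changes in inspired oxygen | s = 5 | s = 10 | s = 15 |
|---|---|---|---|
| 20% down, d = 2 | 0.085 | 0.059 | 0.054 |
| 20% down, d = 5 | 0.251 | 0.104 | 0.074 |
| 50% down, d = 5 | 0.873 | 0.390 | 0.207 |
| 35% down, 15% up, d = 5 | 0.209 | 0.101 | 0.074 |
| 25% down, 25% up, d = 5 | 0.050 | 0.050 | 0.050 |

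For the two mixed rows, with shares down and up, shift = (down − up) × d and total SD = √(s² + (down + up)d² − shift²).

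The rejection rate reaches 10% when 10%, 19% or 29% of infants change in the same direction at d = 5 (s = 5, 10, 15), and when 24%, 47% or 71% do so at d = 2. These are same-direction shares, with nobody changing the other way. Mixed changes add variance: 40% down and 30% up at d = 5, s = 5 gives shift 0.5, total SD √(25 + 17.5 − 0.25) = 6.5 and rejection 0.083, although the net share is also 10%.

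**Would adjustment help?** Suppose a true change of −5, SD 10, and oxygen raised in half the infants, worth +5 points. The unadjusted mean is −5 + 0.5 × 5 = −2.5. If oxygen is raised in response to falling saturation, with latent correlation r, the infants left unchanged are selected on the outcome. Their mean is −5 + r × 10 × 0.798, where 0.798 is the mean of the upper half of a standard normal.

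| r | Unchanged infants | Infants with oxygen raised |
|---|---|---|
| 0 | −5.0 | 0.0 |
| 0.3 | −2.6 | −2.4 |
| 0.5 | −1.0 | −4.0 |
| 1 | +3.0 | −8.0 |

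At r = 0.3 the two groups look alike although the true change is −5. At r = 1 the unchanged group has the wrong sign. A split by oxygen change, or a regression on it, therefore cannot be relied on to remove the bias.

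**The case for a change.** The case for changing the plan is a serious one. The hypothesis attributes the fall to laparoscopy, usual care leaves ventilation free to vary, and the protocol itself admits other influences. Naming the readings at each time would cost a few entries per infant from monitors in use, and one table. It would have to be specified before enrolment to be certain of the reference reading. Nothing in that is wrong, and noting the settings at the four times is good practice.

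It does not amount to a needed change. The table can be built from data the plan already commits to collect, and it leaves the main result as it is. The influences the protocol names, hypercarbia and position, are arguably part of laparoscopy, so that passage does not support the specific bias from inspired oxygen. Nothing shows that settings change between the phases, or by how much.

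The only addition that could alter a conclusion is a trigger for softer wording, such as 10 of 50 infants changing in one direction. That 20% share corresponds to a rejection rate of 25% at d = 5, s = 5, of 10% at d = 5, s = 10, and of 5% at d = 2, s = 15. The count ignores the size of each change and depends on inputs nobody has, so statisticians would reasonably disagree about it.

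**Conclusion.** No change to the plan is called for. The text does leave these readings without assigned times and without an analytic role, but this is a gap that analysts fill sensibly by tabulating the recorded settings beside the oxygenation values. No stated rule or figure is wrong, and the descriptive objective is answered by the unadjusted within-infant change.

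The possible inflation of the false-positive rate runs from none (5%) to 87%. That range rests wholly on assumed shares, effects and SDs, and on a two-time paired t-test standing in for the four-time analysis of variance. It shows that the mechanism is possible; it is not an error rate for this study. What remains is a matter of interpretation: a causal conclusion from a single group under usual care needs cautious wording, whatever the ventilator table shows.
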